APPENDIX 2 – DEFINITION OF ADVERSE EVENTS

Adverse Event

Any untoward medical occurrence in a patient or clinical trial subject participating in the trial which does not necessarily have a causal relationship with the treatment received.

Comment:

An AE can therefore be any unfavourable and unintended sign (including abnormal laboratory findings), symptom or disease temporally associated with the use of a medicinal product, whether or not related to the medicinal product.

Related Event

An event which resulted from the administration of any of the research procedures.

Serious Adverse Event

An untoward occurrence that:

- Results in death (unrelated to original cancer)
- Is life-threatening*
- Requires hospitalisation** or prolongation of existing hospitalisation
- Results in persistent or significant disability or incapacity
- · Consists of a congenital anomaly/ birth defect
- Or is otherwise considered medically significant by the Investigator***

Comments:

The term severe is often used to describe the intensity (severity) of a specific event. This is not the same as serious, which is based on patients/event outcome or action criteria.

* Life threatening in the definition of an SAE refers to an event in which the patient was at risk of death at the time of the event; it does not refer to an event that hypothetically might have caused death if it were more severe.

**Hospitalisation is defined as an unplanned, formal inpatient admission, even if the hospitalisation is a precautionary measure for continued observation. Thus hospitalisation for protocol treatment (e.g. line insertion), elective procedures (unless brought forward because of worsening symptoms) or for social reasons (e.g. respite care) are not regarded as an SAE.

*** Medical judgment should be exercised in deciding whether an AE is serious in other situations. Important AEs that are not immediately life threatening or do not result in death or hospitalisation but may jeopardise the subject or may require intervention to prevent one of the other outcomes listed in the definition above, should be considered serious.

Unexpected and Related Event

An event which meets the definition of both an Unexpected Event and a Related Event.

Unexpected Event

The type of event that is not listed in the protocol as an expected occurrence.

APPENDIX 3 – COMMON TOXICITY CRITERIA GRADINGS

Toxicities which are reportable as a Serious Adverse Event will be recorded according to the Common Terminology Criteria for Adverse Events (CTCAE), version 4.0. The full CTCAE document is available on the National Cancer Institute (NCI) website, the following web address was correct at the time that the protocol was approved:

http://ctep.cancer.gov/protocolDevelopment/electronic_applications/ctc.htm

APPENDIX 4 – SURGICAL COMPLICATIONS & DEFINITIONS

Post-operative complications occurring within 30 days;

- 1. Seroma (breast/axilla) a collection of serosanginous fluid in the wound
 - a. Requiring aspiration 1-2 times
 - b. Requiring aspiration 3 or more times
- 2. Haematoma (breast/axilla) a collection of blood in the wound
 - a. Minor (conservative management)
 - b. Major 1 requiring evacuation in clinic +/- US guidance (no GA)
 - c. Major 2 requiring surgical evacuation (GA)
- 3. Wound infection (breast/axilla)
 - a. Minor (oral antibiotics)(breast/axilla)
 - b. Major 1 (iv antibiotics)(breast/axilla)
 - c. Major 2 (surgical drainage +/- debridement)(breast/axilla)
- 4. Delayed wound healing/skin flap necrosis
 - a. Minor (conservative management)
 - b. Major 1 requiring surgical debridement in clinic (no GA)
 - c. Major 2 requiring surgical debridement in theatre (GA)
- 5. Nipple necrosis
 - a. Minor (conservative management)
 - b. Major 1 (requiring debridement)
 - c. Major 2 (complete NAC loss)
- 6. Wound dehiscence (breast/axilla)
 - a. Minor (conservative management)(breast/axilla)
 - b. Major (requiring return to theatre)(breast/axilla)
- 7. In-hospital complication (including systemic complications
 - a. DVT/PE/MI/LRTI/UTI/transfusion/unplanned HDU/ITU admission
- 8. Readmission to hospital within 30 days
 - a. No
 - b. Yes, for complication listed above (1-7)
 - c. Yes, for other reason

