Study Duration:	Recruitment: 4 years Follow-up: 5 years (extended follow-up to be obtained via routine NHS data linkage)
Trial Office Contact Details:	 SMALL Trial Office, CRCTU, Institute of Cancer and Genomic Sciences, University of Birmingham, [name], UK [name] [name] [contact]

UNIVERSITY^{of} BIRMINGHAM

[@]CRCTU

TRIAL SCHEMA

UNIVERSITY^{OF} BIRMINGHAM

Protocol

SCHEDULE OF EVENTS

Assessment	Screening	Trial Entry	Trial Treatment (within 31 days of randomisation)	Following Trial Treatment	Additional Surgical Treatment as Indicated	Post Completion of Trial Treatment	6-Month Follow-up	Annual Follow-up Years 1-5
Diagnostic biopsy and histology	х							
Axillary US scan +/- FNAC or core biopsy	х							
Molecular markers ER PR HER2	X X X							
Medical history and physical examination including height and weight	х		Appropriate surgery		Re-excision of margins or			
Informed consent for Information Study (optional)*	х		according to		mastectomy for Surgery			
Informed consent for trial entry		Х	including axillary		Arm patients			
Baseline Quality of Life questionnaires*		Х	node biopsy					
Randomisation		Х						
Tumour sample collection (VAE arm only)						х		
Related Adverse Event review					Surgical	х	х	х
Reporting of: survival, disease progression, development of new breast disease			OR		excision for VAE Arm		х	х
Tumour sample collection for confirmed recurrence (VAE arm only)					radiological evidence of		х	х
Post-VAE mammogram (VAE arm only)			Vacuum assisted excision and	х	incomplete excision plus			
Radiotherapy as per local guidelines ^{\$}			insertion of		sentinel lymph	х		
Adjuvant endocrine therapy as per local guidelines			marker clip		node biopsy	х	х	х
Quality of Life questionnaires*							Х	Х
Annual mammography								х
Investigations for and treatment of ipsilateral/contralateral disease as per local protocol							Х	х

Discussions with patients will be audio recorded as part of the Information Study (consenting patients only)

* Patients consenting to the Quality of Life Sub-study only. Baseline QoL Questionnaire Booklets completed at clinic, subsequent questionnaires will be sent from the SMALL Trial Office

^{\$} Radiotherapy should commence within 8 weeks following breast conserving surgery and ideally within 31 days

ABBREVIATIONS

СВ	Core biopsy
CRCTU	Cancer Research UK Clinical Trials Unit
CRF	Case Report Form
ER	Oestrogen receptor
ERDC	Electronic Remote Data Capture
ET	Endocrine therapy

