7.2.2.1 Vacuum assisted excision

Please refer to the SMALL Radiology Manual for detailed guidance on the VAE procedure. Patients randomised to this arm of the trial will undergo VAE of their breast cancer under local anaesthesia as an out-patient procedure. It is expected that VAE will be performed within 31 days of randomisation. VAE may be carried out under either ultrasound or stereotactic guidance. All cores taken at VAE should be submitted for histopathological assessment, with number of cores and total weight recorded on the CRF. VAE should be carried out by appropriately-trained individuals carrying this out as part of their routine clinical practice. Post-VAE a marker clip should be inserted and a post-VAE mammogram carried out (lateral/mediolateral oblique and cranio-caudal views). The procedure report should stipulate the needle gauge used, number of cores taken and the type of marker clip placed in the breast, together with the operator's impression of the completeness of excision. The post-VAE mammogram report should state whether the lesion remains visible. If no lesion is visible then complete excision of the lesion is assumed. If the lesion remains visible then surgical excision will be required, in these cases please also forward a copy of the patient's anonymised pathology report to the SMALL Trial Office.

If interpretation of the post-VAE mammogram is unclear due to the presence of haematoma then a repeat mammogram should be carried out at 4 weeks post-procedure. If haematoma remains present at this stage then repeat ultrasound should be carried out with aspiration of the haematoma. Subsequently a further repeat mammogram should be carried out. If at this stage the lesion is resolved then complete excision is assumed. A persistent lesion should be assumed to be residual disease and the patient should proceed to surgical excision.

Where there is uncertainty at a local level regarding completeness of excision, a radiological second opinion can be provided through the Radiological Second Opinion Service (see below, Section 7.2.3.3).

Patients undergoing VAE only in the VAE arm will not undergo any axillary procedure in addition to their axillary ultrasound carried out as part of their diagnostic assessment. Patients proceeding from VAE to surgical treatment due to radiological assessment of incomplete excision should undergo axillary staging using sentinel lymph node biopsy.

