16.2.2 Definition of Secondary outcome measures

Complications arising from surgery or VAE

This is defined as complications occurring within 30 days of protocol defined surgery or VAE. Possible complications are expected to include seroma, haematoma, wound infections, delayed wound healing, skin flaps necrosis, nipple necrosis, wound dehiscence, in hospital complications, hospital readmission and unplanned re-operations, and these are defined in Appendix 4.

Time to ipsilateral breast cancer recurrence

This is defined in whole days as the time from randomisation until first report of ipsilateral invasive disease. Randomised patients with no evidence of disease will be censored at the date of last clear mammogram or date of death.

Time to development of contralateral invasive breast cancer

This is defined in whole days as time from randomisation until first report of contralateral invasive disease. Randomised patients with no evidence of disease will be censored at the date of last clear mammogram or date of death.

Overall survival time

This is defined in whole days as time from randomisation until date of death from any cause. Patients who remain alive during the course of the study will be censored at the date last known to be alive.

Quality of life

The assessment utilities being used are defined in Section 8.1. These will all be scored at each timepoint utilising the specific scoring schemes for each type of questionnaire which will produce scores across multiple themes and domains.

QALY

This will be calculated from the EQ5D QoL questionnaire and will be utilised in the Health Economic analysis (see Section 9).

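### Appendix 4 sets no clinical threshold for haematoma and only the VAE arm is imaged within 30 days, so haematomas seen only on imaging can raise the VAE complication rate

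*Protocol*

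**What the plan says.** Section 16.2.2 defines the first-listed secondary outcome as "complications occurring within 30 days of protocol defined surgery or VAE" and refers to Appendix 4 for the individual complications. One list and one window serve both arms.

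Appendix 4 treats the two fluid collections differently:

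- **Item 2** is headed "Haematoma (breast/axilla) a collection of blood in the wound". It has a minor grade for conservative management and two major grades for evacuation in clinic or in theatre.
- **Item 1** is headed "Seroma (breast/axilla) a collection of serosanginous fluid in the wound". Its grades start at "Requiring aspiration 1-2 times", and the only other grade is three or more aspirations.

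The Schedule of Events restricts the post-VAE mammogram to the VAE arm, and Section 7.2.2.1 asks for it after every VAE. Where the film is "unclear due to the presence of haematoma then a repeat mammogram should be carried out at 4 weeks post-procedure". If the haematoma is still there, ultrasound with aspiration and a further mammogram follow. Section 7.1 gives the surgery arm annual mammography and no earlier breast imaging.

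In Section 13.1 the VAE form collects the post-procedure radiology, including repeat imaging and haematoma aspiration. Its submission schedule also allows 30 days for reporting surgical complications.

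**The concern.** A definition shared by both arms gives a fair comparison only if the events it covers are equally likely to be found in both. Item 2 covers any haematoma, however small and whether or not the woman or an examiner notices it. One arm has routine imaging that can show such collections, and the other has none until the first annual mammogram. Applied literally, the definition sets imaging plus clinical detection after VAE against clinical detection alone after surgery.

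Post-procedure complications are the first secondary objective in the synopsis, and Section 1.2.1 names a possible reduction in surgical complications as a benefit of VAE. Section 16.5 also sends complications data to the data monitoring committee. An excess of minor haematomas created by imaging would work against that potential benefit. Section 16.3 plans only a description by arm, so the outcome definition is the main protection against unequal detection.

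**Working it through.** The protocol states no haematoma or seroma rate, so there is no planned figure to reproduce. The check compares the rules by arm and then illustrates the size under stated assumptions.

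**Step 1: what can be found and graded within 30 days**

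| Finding | VAE arm | Surgery arm |
|---|---|---|
| Haematoma, clinically evident, left alone | graded 2a | graded 2a |
| Haematoma, silent, left alone | imaging can show it; fits 2a as worded | no protocol imaging; not looked for |
| Seroma, not aspirated | meets the heading, no grade | meets the heading, no grade |

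Only the second row differs by arm. The 4-week repeat falls at 4 × 7 = 28 days, inside the 30-day window.

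**Step 2: size, first illustration**

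Inputs: 533 VAE and 267 surgery women (Section 16.7). Assumed: 5% have a clinically evident haematoma in each arm; a silent haematoma is visible on imaging in a share x of the remaining VAE women; sites score a share s of these as 2a.

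- VAE rate = 0.05 + 0.95·x·s
- Spurious excess = 0.95·x·s
- Standard error = √[p(1−p)/533 + 0.05·0.95/267], where p is the VAE rate; 95% interval = excess ± 1.96 × standard error

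With s = 1 the surgery arm stays at 5% (13 of 267) and there is no true difference:

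| x | VAE rate | VAE count of 533 | Excess, points (95% interval) |
|---|---|---|---|
| 0% | 5.0% | 27 | 0 (−3.2 to 3.2) |
| 2% | 6.9% | 37 | 1.9 (−1.5 to 5.3) |
| 3% | 7.85% | 42 | 2.9 (−0.6 to 6.3) |
| 5% | 9.75% | 52 | 4.75 (1.1 to 8.4) |
| 10% | 14.5% | 77 | 9.5 (5.5 to 13.5) |
| 20% | 24.0% | 128 | 19.0 (14.5 to 23.5) |
| 30% | 33.5% | 179 | 28.5 (23.7 to 33.3) |

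Example for x = 5%: √(0.0975 × 0.9025/533 + 0.0475/267) = 0.0185, and 1.96 × 0.0185 = 0.036, giving 4.75 ± 3.6 points.

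If s = 0 the excess is zero for every x. If half are scored, x = 10% gives 0.95 × 0.10 × 0.5 = 4.75 points.

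**Step 3: size, second illustration**

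Assume the same true rate h of untreated haematoma in both arms, all found and scored after VAE, and a share d found after surgery. The excess is h(1−d).

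| h | d = 100% | d = 50% | d = 25% |
|---|---|---|---|
| 5% | 0 | 2.5 points | 3.75 points |
| 10% | 0 | 5 points | 7.5 points |
| 20% | 0 | 10 points | 15 points |

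At h = 10% and d = 50%, about 53 of 533 VAE women are graded against about 13 of 267 surgery women (27 with full detection). Surgical haematomas are under-counted here, not removed.

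**Step 4: aspiration to clear the image**

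Section 7.2.2.1 has a persisting haematoma aspirated so that the mammogram can be read. Item 2b covers evacuation in clinic with or without ultrasound guidance, so this step could be graded major 1, and only in the VAE arm. Because it follows the 4-week film, only 30 − 28 = 2 days of the window remain, so many such aspirations may fall outside it. The protocol does not say how they are to be graded.

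**The case against.** The strongest reply is that the protocol nowhere instructs sites to score a haematoma seen only on the mammogram. Section 7.2.2.1 mentions haematoma only as a reason to repeat imaging. Section 12.1.1 limits reporting to related events that patients experience. Section 13.1 has a separate Adverse Event form for treatment complications. The Radiology Manual and the form completion guidelines, which are not at hand, may contain a recording rule. This stands in part: scoring is a permitted reading of item 2a, not a mandated one. It does not remove the point, because no section excludes imaging-only findings, and the VAE form takes the radiology and the 30-day complications together. Sites must decide for themselves, and the question arises routinely in one arm only.

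The reply on size also stands. The rates above are assumptions, and at 2% or 3% silent haematoma the interval includes zero. The outcome is reported without a test, no composite total is defined, and an excess confined to the mildest grade would be visible if results are tabulated by grade.

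A reader might infer something stronger: that untreated collections as a whole count against VAE and vanish after surgery. The documents do not support that. A surgical haematoma found clinically and left alone is graded 2a, exactly as after VAE. An unaspirated seroma lacks a grade in both arms, and Section 7.2.2.4.1 foresees persistent seroma in the VAE arm. The seroma gap would favour one arm only if seroma rates differed, and the protocol gives none. Such a seroma still meets the heading of item 1, so it lacks a grade but is not clearly barred from being recorded.

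**Conclusion.** The point holds in a limited form. Item 2 has no clinical threshold, and protocol imaging within 30 days exists in the VAE arm only, so ascertainment of silent haematoma is unequal and can inflate the VAE minor-haematoma rate. The direction follows from the imaging schedule; the size cannot be derived from the documents. It runs from zero, if imaging-only findings are not scored, to tens of percentage points, if silent haematoma is common and always scored.

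The consequence is confined to a descriptive secondary outcome, mainly its mildest haematoma grade. Neither re-excision nor local recurrence-free survival is touched. It is not shown that a true benefit of VAE would be hidden or reversed.

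The absent no-intervention grade for seroma is a separate inconsistency within Appendix 4, whose items 2, 4, 5 and 6 all have a conservative-management grade. It has no documented direction of bias.

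**What to change.** In Appendix 4 and the form guidance, apply one threshold to both arms: a haematoma or seroma counts as a 30-day complication only if it is clinically evident (reported by the patient or found on examination) or treated for symptoms or signs.

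Record collections seen only on the post-VAE or 4-week mammogram, and any aspiration done only to make the mammogram readable, on the VAE form as now, with a marker to identify them. Report them separately as imaging findings, outside the between-arm complication table.

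Optionally, for consistency, add a no-intervention grade to the seroma item.

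The cost is wording in Appendix 4 and a tick-box or completion note on the procedure forms. It needs no extra visits, imaging or patients and changes no clinical management. The headline table will hold fewer minor events, but the imaging-only ones remain visible in their own table. The marker is best added before data accumulate, since the two kinds of haematoma may be hard to separate afterwards.

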APPENDIX 5: RADIOTHERAPY QUALITY ASSURANCE

A radiotherapy quality assurance programme is an integral component of any radiotherapy trial. The NCRI Radiotherapy Trials Quality Assurance (RTTQA) group will be responsible for implementing and coordinating the PRIMETIME Radiotherapy Quality Assurance (RTQA) programme.

The planning and delivery of radiotherapy for SMALL will reflect radiotherapy practice developed as part of the IMPORT and FAST-Forward trials which represent the modern standard for breast cancer radiotherapy practice in the UK.

The SMALL Radiotherapy Quality Assurance (RTQA) programme:

The SMALL RTQA programme is comprised of two parts, a pre-study and an on-study component. In light of the comprehensive RTQA programmes associated with the afore mentioned radiotherapy breast cancer trials, radiotherapy centres may be eligible to undertake a streamlined pre-study RTQA programme based on participation in the IMPORT or FAST-Forward trials.

If a radiotherapy centre has undertaken and received pre-trial QA approval for either the IMPORT or FAST-Forward trials, centres will be granted RTTQA approval without any additional QA procedures requested. If a centre has not previously undertaken and received pre-trial RTQA approval for either the IMPORT or FAST-Forward trial, a centre will be required to complete a Facility Questionnaire and submit a 'dummy run' case for review by RTTQA.

Flow diagram summarising RTQA review for SMALL:

*Additional information may be requested by RTTQA.

Pre-study QA:

A. Facility Questionnaire

The Facility Questionnaire must be completed by a member of the radiotherapy staff and submitted to the QA team. The questionnaire will cover details of treatment technique, immobilisation, verification and dosimetry.

B. Dummy Run

Centres should choose one of their own patients to submit to the RTTQA group for technique review. A patient, where the breast only has been treated with radiotherapy, should be selected.

On-study QA:

C. Ongoing Data Collection

Radiotherapy plans (CT data, structure set, plan and dose files) may be collected electronically by the QA team if requested by the SMALL study team, TMG or DMC based on the recurrence rates seen in the study.

Analysis of Radiotherapy data for QA programme:

The radiotherapy data from the quality assurance programme may be analysed independently from the main study. Discrepancies from standard of care treatment will be audited and discussed with the Chief Investigator and participating centres.

APPENDIX 6 - QUINTET RECRUITMENT INTERVENTION (INFORMATION STUDY)

The SMALL trial will employ an integrated QuinteT Recruitment Intervention (QRI) aimed at optimising recruitment and informed consent^{41,42}. The trial aims to recruit across a large number of centres, and the recruitment pathway is likely to be multi-disciplinary. Recruitment challenges may arise in relation to flagging up eligible patients, differences in levels of recruiters' equipoise and patients' preference for open surgery or VAE. The QRI in the SMALL trial is aimed at identifying such recruitment difficulties as they emerge and implementing interventions to address them throughout the recruitment period over four years. The QRI will begin in the internal pilot phase (months 1-6 of active recruitment), and will initially be carried out in a small, diverse sample of centres (in terms of centre size, early recruitment figures/practices, etc.), with concurrent reviews of other centres. This will enable an in-depth understanding of recruitment challenges early on, and the development of tailored solutions, which can be applied to other centres, alongside continued identification of recruitment challenges as they occur in the pilot phase (months 7-18). It is anticipated that this multi-faceted approach to recruitment will enable a smooth transition into the main phase of the trial (months 19-24), which will continue to be carefully investigated employing the QRI methods until recruitment is completed (months 25-48). The QRI has been demonstrated to be most effective at optimising and sustaining recruitment when integrated throughout the recruitment phases of a trial, as proposed for SMALL.

The QRI uses novel qualitative and mixed-method approaches pioneered during the HTA-funded ProtecT study⁴³. These methods have since been refined and applied to several other RCTs in different clinical contexts, leading to insights about recruitment issues and development of targeted recruitment strategies⁴⁴. The QRI will proceed in two iterative phases.

Phase I: Understanding Recruitment

Phase I aims to understand the recruitment process in clinical centres and will comprise one or more of the following:

• Mapping of eligibility and recruitment pathways for clinical centres

Detailed pathways will be compiled noting the points at which patients receive information about the trial, which members of the clinical team they meet and the timing/frequency of appointments. These will be compared with details specified in the trial protocol and pathways from other centres to identify practices that are potentially more/less efficient. The QRI researcher will also work closely with the CTU to compose detailed logs of potential participants documenting the numbers of screened, eligible, approached and randomised patients (SEAR approach)⁴⁵. Adherence to treatment allocation amongst those randomised and reasons for non-participations amongst decliners will also be noted. These will help identify points at which patients do not continue with recruitment to the RCT across centres and be considered in relation to estimates specified in the grant application/study protocol.

• Audio-recording and observations of recruitment discussions

Scheduled face-to-face appointments and telephone conversations during which the trial is discussed will be routinely audio-recorded on an encrypted device (and if necessary, observed) with written consent. Recordings will be used to explore information provision in relation to key study concepts and treatment options, recruitment techniques, management of patient treatment preferences, and randomisation decisions to identify recruitment difficulties and improve information provision. Recordings will be collected by trial staff across centres and transferred to/from the University of Bristol through University of Bristol-approved secure data transfer facilities or encrypted flash drives that adhere to NHS Trust policies.

• In-depth interviews

Semi-structured interviews will be undertaken with:

• Members of the Trial Management Group (TMG), including the Chief Investigator and those involved in design and management of the trial (n=4-5)

Page 46 of 49

- Clinicians/recruiters involved in the patient pathway (n=20-25)
- Eligible patients approached to take part in the trial (n=5-10)

Interviews with TMG members/recruiters will explore key topics such as their perspectives on the trial design, protocol, evidence base for the trial, uncertainty/equipoise in relation to the RCT arms, how the arms/protocol are delivered in their clinical centre, methods for identifying eligible patients, views on eligibility, and examples, if any, of actual recruitment successes/difficulties. Interviews with patients will explore views on the presentation of study information, understanding of trial processes (e.g. randomisation), and reasons underlying decisions to accept or decline the trial. Interview and audio-recording data will be compared to identify differences in reported and actual recruitment practices amongst recruiters and, if necessary, differences in levels of understanding amongst patients. The numbers specified above are estimates based on previous QRIs and the precise numbers will be guided by the concept of data saturation (when no new information is forthcoming) and other pragmatic considerations.

All interviews will be audio-recorded on an encrypted device, and take place at a mutually convenient location, in a suitably private and quiet setting. Participants will be offered the option to be interviewed over the telephone. The University of Bristol's 'lone researcher' safety policies will be adhered to for any interviews taking place in non-public settings (e.g. participants' homes).

• Observation of TMG and investigator meetings

The QRI researcher will regularly observe and make detailed notes of study meetings to gain an overview of trial conduct and overarching challenges. These meetings may be audio-recorded, with informed consent.

• Study documentation

The QRI team will work closely with the CTU to ensure that patient-facing study documents are unbiased and clear. As the study progresses, patient information sheets (PIS) and consent forms will be compared with interviews and recorded appointments, to identify any disparities or improvements that could be made.

Phase II: Development and Implementation of Recruitment Intervention Strategies

The QRI team, with the CI and TMG, will formulate a 'plan of action' to improve recruitment and information provision, grounded in findings from phase I. Generic forms of intervention may include 'tips' documents providing suggestions on how to explain the trial design and processes. Supportive feedback will be a core component of the plan of action, with the exact nature and timing of feedback dependent on issues that arise. Centre-specific feedback may cover institutional barriers, while multi-centre group feedback sessions may address widespread challenges that would benefit from discussion. As the SMALL trial will have a large number of centres, the QRI team may combine them in regional clusters for feedback. All group feedback sessions will be aided by displaying anonymised data extracts from interviews and audio-recorded appointments. Individual confidential feedback will also be offered – particularly where recruiters experience specific difficulties, or where there is a need to discuss potentially sensitive issues. Investigator meetings/teleconferences and site visits from the CI/TMG members may also be employed to discuss technical or clinical challenges related to the trial (e.g. discomfort surrounding eligibility criteria).

Evaluating Changes in Recruitment Figures and Practice

Recruitment figures (numbers of screened, eligible, approached and randomised patients) will be assessed before and after the 'plan of action' is implemented, and regularly monitored thereafter to assess changes. Continued targeted investigation of recruitment issues and delivery of feedback/training will be undertaken as necessary, with particular focus on changes in recruitment practice before and after the intervention.

Consent Processes for the QRI

Healthcare professional consent

Recruiting staff and TMG member consent will be obtained through a 'master' consent form that covers all aspects of the QRI. Research nurses or the QRI researcher will obtain written consent from all staff. This will be a one-off process to cover consent for all future recordings of appointments, interviews, and observations of TMG/investigator meetings throughout the study.

Patient consent

Audio recording/observing recruitment appointments:

Information about the QRI is provided to patients in the Information Study Patient Information Leaflet. Recruiters will check if the patient has any questions about the audio-recording process at the first recruitment appointment, and seek written consent to record the discussion. Patients who agree will sign a one-off QRI consent form that seeks permission to record future discussions about the trial in the lead up to the patient making their decision about participation.

Interviews:

The QRI consent form will include a clause that asks patients if they would be willing to take part in a future research interview ('Yes' or 'No'). Patients who select 'Yes' may then be approached by the QRI researcher.

Analysis of QRI Data

Audio-recordings of interviews and appointments will be transcribed verbatim in full or in parts (targeted) either by a University of Bristol employee or by a University of Bristol approved transcribing service. Transcripts will be edited to ensure anonymity of respondents and stored securely, adhering to the university's data storage policies.

Interview data will be managed using qualitative data analysis software (such as NVivo, QRS International), and analysed thematically using constant comparative approaches derived from Grounded Theory methodology⁴⁶. Audio-recorded recruitment appointments and follow up discussions will be subjected to content, thematic, and novel analytical approaches, including aspects of targeted conversation analysis⁴⁷ and appointment timing (the 'Q-QAT method')⁴⁸. There will be a focus on aspects of information provision that are unclear, disrupted, or potentially detrimental to recruitment and/or adherence. Analysis of QRI data will be led by the qualitative RA with the guidance of the QRI lead, with a sample of transcripts independently coded by both researchers.

Key issues identified from the observation notes of appointments and TMG/investigator meetings will be considered alongside other qualitative findings. Findings from all sources will be drawn together in a descriptive account that will be presented to the CI/TMG and will form the basis for the 'plan of action' (Phase II above).

TRIAL OFFICE

Cancer Research UK Clinical Trials Unit Institute of Cancer and Genomic Sciences University of Birmingham [name]

ENQUIRIES

2 [contact]

PATIENT RANDOMISATION

Via Erdc: https://www.cancertrials.bham.ac.uk

Or Call:

🖀 [name] or 🖀 [name]

